3.1 Summary of Prior Clinical Experience

LiteCure conducted two studies on the safety and efficacy of NIR-TLT applied to the forehead (prefrontal cortex) twice a week in subjects with MDD. The device used for ELATED-2 is a predicate device for EXPi-laser.

ELATED-1 was a 3-week proof-of-concept study of TLT (EXPi - class IV laser, wavelength 808 nm; irradiance 700 mW / cm²; fluence 84 J / cm²; total energy 2.4 kJ per session for 6 sessions) All subjects (n = 4) were treated with TLT. Mean baseline HAMD-17 scores for depression decreased from 19.8 ± 4.4 (SD) to 13 ± 5.35 (SD) after treatment ($p = 0.004$) (Cassano et al. 2015). (Cassano et al. 2015).

Near Infrared Transcranial Laser Therapy in Subjects with Major Depressive Disorder: A study of Dosing with Laser.

ELATED-2 was an 8-week double-blind, randomized, controlled study of TLT (Omnilux New U - LED, 823 nm; 36.2 mW / cm²; up to 65.2 J / cm²; vs. sham for 16 sessions). At completion, the mean HAMD-17 for depression decreased 11.7 ± 7.5 points (TLT, n = 9) vs. 5.3 ± 7.0 points (simulation, n = 9) (p = 0.04); the differences were even more pronounced in the completer sample as HAMD-17 decreased 15.7 ± 4.4 (TLT, n = 6) points vs. 6.1 ± 7.9 points (simulation, n = 7) (p = 0.01). (Cassano et al., 2018).

3.2 Overview of LiteCure Laser System

The EXPi device is a research device based on LiteCure's EXPi Deep Tissue Laser Therapy™ system. For this research study, the EXPi system's beam delivery, Empower™, is modified to deliver NIR laser energy non-invasively to the brains of subjects diagnosed with neuropsychiatric disorders. Other than the cap, the EXPi device is the same device as LiteCure's EXPi system: model LTS-2500, which is marketed under FDA 510(K) # K173067. The device is manufactured and supplied by LiteCure LLC, [name].

The EXPi device is a Class II medical device according to 21 CFR 890.5500 and 878.4810 and is manufactured according to 21 CFR 820. It uses laser diode sources that emit in the near infrared (808 +/- 10 nm) with a maximum continuous output of ≤ 30 watts. The device consists of two main assemblies: a console and an optical delivery system. Laser power is generated and controlled within the console assembly and delivered to the optical delivery system: custom helmet (cap), via a flexible double-clad optical fiber. The cap is configured to produce a 4 cm diameter (12 cm²) beam of light at each of two sites on the subject's forehead: adjustable at/near EEG locations F3 and F4.

The console is programmed to produce laser energy in one of 4 modes:

1. Mode 1 (BCW group), NIR-TLT dose:
 - i. Treatment site(s): EEG F3 and F4
 - ii. Time format:
continuous wave
 - iii. Average radiance: 350 mW / cm²
 - iv. Exposure time: 429 sec.
 - v. Total fluidity delivered: 3.6 kJ (1.8 kJ per treatment location)
2. Mode 2 (BPW-1 group), NIR-TLT dose:
 - i. Treatment site(s): EEG F3 and F4
 - ii. Time format: wave
pulsed, 10 Hz; 50% duty cycle
 - iii. Average radiance: 350 mW / cm²
 - iv. Exposure time: 429 sec.
 - v. Total fluidity delivered: 3.6 kJ (1.8 kJ per treatment location)
3. Mode 3 (BPW-2 group), NIR-TLT dose:
 - i. Treatment site(s): EEG F3 and F4
 - ii. Time format: pulsed wave, 40-50 Hz; 50% duty cycle
 - iii. Average radiance: 350 mW / cm²

Near Infrared Transcranial Laser Therapy in Subjects with Major Depressive Disorder: A study of Dosing with Laser.

- iv. Exposure time: 429 sec.
- v. Total fluidity delivered: 3.6 kJ (1.8 kJ per treatment location)

4. Mode 4 (SHAM group), NIR-TLT dose:

- i. Treatment site(s): none
- ii. Time format: none
- iii. Average radiance: 0 mW / cm²
- iv. Exposure time: 429 sec.
- v. Total fluidity delivered: 0 kJ

See section 4.3 - Dosing rationale

The console display does not provide information on the dose irradiance, showing only the mode number, e.g. Mode 1 and, although the laser exposure varies with the treatment mode, to maintain blinding, the treatment time will be the same in all modes: 429 seconds (7.15 minutes). In addition, the behavior of the device, the performance/output of all visible and audible indicators, including the graphical user interface, is identical in all modes, differing only with respect to treatment irradiance. Since the laser radiation emitted during the NIR mode is invisible to the naked eye, the modes cannot be distinguished from each other, which keeps the operator and subject blinded to the group tasks.

Dose administration for the present trial will follow the specifications: wavelength 830 nm; mean irradiance 54.8 mW / cm²; mean fluence 65.8 J / cm² (according to the parameters used in the ELATED-2 study in MGH with the Omnilux New U device), which demonstrated in terms of improvement of depressive symptomatology evaluated with HAMD17 in patients with major depression. Therefore, by virtue of the ELATED2 findings, doses were considered for this intervention in patients with MDD.

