Study Design:	
Multi-center, randomized, sham, double-blind.
 
This trial will randomize 112 subjects into 4 equal groups: bilateral continuous wave (BCW), bilateral pulsed wave (BPW 1-2) and SHAM. All subjects, investigators (except the study statistician) and outcome assessors will be blinded to group assignments. The device operator will be aware of group assignments.
 
All subjects will receive 3 NIR-TLT sessions per week for 6 weeks. A follow-up evaluation will be performed 2 weeks after the end of the study. The treatment will follow these specifications: wavelength 830 nm; average irradiance 54.8 mW / cm²; average fluence of 65.8 J / cm² (according to the parameters used in the ELATED-2 study at MGH with the Omnilux New U device), being the total fluence delivered: 3.6 kJ (bilateral) or 1.8 kJ (unilateral), either on the subject's forehead, at or near the electroencephalography (EEG) sites F3 and F4.
 
All NIR-TLT sessions will be 429 seconds (7.15 minutes), regardless of group assignment.

Study population:	
Patients eligible to participate in the study will be diagnosed with MDD by DSM criteria (MINI). Subjects will be between 18 and 75 years of age (not yet 76 years of age) on the date of the examination.

Duration of participation:	
Research subjects will remain in the study for 8 weeks. (6-week treatment period, plus 2-week follow-up). The total duration of the study will be 24 months.

Near Infrared Transcranial Laser Therapy in Subjects with Major Depressive Disorder: A study of Dosing with Laser.

Criteria for valuation:

- **Main:** Improvement of depressive symptoms from each of the four doses of NIR-TLT. Assessed using HAMD-17, at 3 time points (visit 1, visit 9 and visit 18).
- **Secondary:** Safety and tolerability. Assessed by SAFTEE- SI (self-assessed), and collection of serious adverse events throughout the study. Safety data will be used to assess the tolerability of each of the NIR-TLT doses.
Changes in brain electrophysiology (electrical activity): Commercially available EEG devices will be used to collect data on brain electrical activity. At 3 time points (visit 1, visit 9 and visit 18).
- Changes in measurements of MDD symptom severity assessment scales:
 - Doctor Administered Scales: QIDS-C and CGI-S
 - Patient-reported scales: ASQ and SDQ

Entry Criteria:

Inclusion Criteria

1. The age of the subjects in the examination will be between 18 and 75 years (inclusive).

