4.4.1 Randomization procedure

At screening, participants will be assigned an identification number on a first-come, first-served basis. When it is confirmed that the participant is eligible for the clinical trial, he/she will be randomized.

The assignment of each participant to a particular treatment arm (experimental and control group will be performed in a 1:1:1:1 ratio) will be done by using an electronic system, which is centrally administered.

Near Infrared Transcranial Laser Therapy in Subjects with Major Depressive Disorder: A study of Dosing with Laser.

For each participant at each visit, the investigator or center coordinator will communicate with the central statistician and, through a user and password assigned for the center, will enter the web system where he/she will be able to request and obtain the corresponding treatment number assigned to him/her in the study, and then proceed with the laser application. The participants and the study investigator will be blinded to the treatment assignment. The screen of the medical device does not show information of the dose applied to each participant, only the group to which he/she belongs will be referenced, keeping the dosing details confidential.

At central level, the unblinded statistician (responsible for administering this web system) will know which treatment arm corresponds to each participant from each research center.

4.4.2 *Blinding procedure*

This study is a clinical trial where blinding of both the investigator and the study participant will be assured. Only the treatment identifiers, the central statistician of the study, will know the treatment identifiers.

The sponsor is responsible for providing the medical device under study, programming and maintenance of the device.

The investigator at each center will be responsible for providing the corresponding dose according to the intervention under study (treatment assigned by the statistician through the web system) to each study participant.

Simulation blinding will be effective because the radiation is not visible and because no dose from the NIR-TLT will produce any perceptible difference from the simulation patient, e.g., skin heating.

4.4.3 *Contingency plan for opening of the blind*

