5.1 General Considerations

It is expected that multiple sites, randomized, sham-controlled, double-blinded, double-blinded trials will include 112 patients, randomized into four groups. Each group will receive a different dose of NIR-TLT. Group tasks and dosing will be blinded to doctors, patients and outcome assessors. Device operators will be aware of the group assignments.

The purpose of this study is to compare the antidepressant effect of four different doses of NIR-TLT and to correlate this effect with the effects of the individual dose on brain electrophysiology and mitochondrial function.

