6.6 Informed Consent

The Principal Investigator will be responsible for developing the Informed Consent Form to be prepared in accordance with FDA 21 CFR Part 50 for all U.S. sites. The Informed Consent Form will be used to explain in simple terms, before the subject enters the study, the potential risks and benefits to the subject. The Informed Consent Form will contain a statement that consent is freely given, that the subject is aware of the risks and benefits of entering the study, and that the subject is free to withdraw from the study at any time.

Prior to a subject's participation in the study, the written informed consent form will be signed and dated personally by the subject or by an individual authorized to sign on behalf of the subject in accordance with local regulations.

If a subject is unable to read or if a legal representative is unable to read, an impartial witness will be present during the entire discussion of the Informed Consent Form. After the Written Informed Consent Form and any other written information provided to the subject is read and explained to the subject or legal representative, and the subject has given oral consent for participation in the study, the witness will sign and date the consent form.

Transcranial Near Infrared Laser Therapy in Subjects with Major Depressive Disorder: A Laser Dosing Study.

A witness in the consent process is considered an unbiased individual independent of the study.

Note: The investigator should document the acquisition of the written informed consent form in the subject's medical records, and the subject or legal representative should receive a copy of the informed consent form document prior to enrollment in the study.

6.7 Adherence to Protocol.

The protocol must be read and followed by all personnel participating in the study.

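### Section 3.2 says the operator is kept blinded, but the console shows a mode number whose arm the protocol prints; Sections 1 and 5.1 say operators are aware, and nothing bars an operator from rating

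*Protocol*

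**What the plan says.** **On the operator.** Section 3.2 says of the device: "The console display does not provide information on the dose irradiance, showing only the mode number, e.g. Mode 1". It then concludes that "the modes cannot be distinguished from each other, which keeps the operator and subject blinded to the group tasks". The list just above that text names the arm for each of the four modes; the last entry is headed "Mode 4 (SHAM group), NIR-TLT dose". Section 4.4.1 says the device screen "does not show information of the dose applied to each participant, only the group to which he/she belongs will be referenced". Section 6.7 adds: "The protocol must be read and followed by all personnel participating in the study". Section 1 says "The device operator will be aware of group assignments" and Section 5.1 says "Device operators will be aware of the group assignments".

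**On investigators, doctors and raters.** Section 5.1 says "Group tasks and dosing will be blinded to doctors, patients and outcome assessors". Sections 1, 4.4, 4.4.1, 4.4.2 and 4.11 also declare investigators blinded, and Section 4.13 has the scales administered by doctors who do not know the allocation.

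**On who is at the device.** In Section 4.4.1 the investigator or the site coordinator obtains the treatment number at each visit and goes on to the laser application. Section 4.4.2 makes the investigator responsible for providing the assigned dose. Section 6.5 restricts application to the principal investigator or a trained designee. Section 4.20.1 refers to a study doctor in the treatment room. Section 4.9.2 limits the room to the participant and the staff giving the treatment. The table in Section 8 marks treatment with the research associate's symbol and HAMD-17, QIDS-C and CGI with the doctor's.

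**The concern.** The protocol gives two opposite answers to whether the person running the device knows the arm. The answer that claims blinding rests on the modes being indistinguishable, yet the screen labels them and the protocol supplies the key.

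This matters because the primary outcome, HAMD-17, is scored by a doctor from an interview. A rater who knows whether the participant is on sham or on an active mode can be influenced by it. The comparison between arms is therefore protected only if whoever sees the console is not the person who scores that participant. The protocol states the intended outcome, that raters are unaware, but leaves open routes by which a doctor or investigator could see the arm, and it has no rule that closes them.

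**Working it through.** No arithmetic applies. The passages are set side by side.

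**Step 1: can the operator tell the modes apart?**

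| Element | Where | Content |
|---|---|---|
| Display | Section 3.2 | The mode number is shown |
| Key | Section 3.2, list of modes | 1 = BCW, 2 = BPW-1, 3 = BPW-2, 4 = SHAM |
| Who reads the key | Section 6.7 | All study personnel |
| Screen content | Section 4.4.1 | The participant's group is referenced |
| Claim of blinding | Section 3.2 | Operator blinded |
| Opposite claim | Sections 1 and 5.1 | Operators aware |

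The display plus the key identifies the arm, sham included. Invisible radiation and identical indicators can help to blind the participant, but they cannot blind someone who reads the mode number and knows the list. The protocol does not say that displayed numbers are scrambled or differ from that list. Section 4.4.2 adds to the conflict by reserving knowledge of the treatment identifiers to the central statistician, which does not fit operators who are aware.

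**Step 2: can someone declared blinded reach the console?**

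- Section 6.5 lets the principal investigator apply the laser in person. Investigators are declared blinded.
- Section 4.4.1 takes the investigator or coordinator from obtaining the treatment number to the laser application. The responsibility for dosing in Section 4.4.2 may mean oversight only, so it carries less weight.
- Section 4.20.1 puts a study doctor in the treatment room. Read with Section 4.9.2, which admits only the participant and the staff giving treatment, that doctor is one of the treating staff. Doctors are declared blinded in Section 5.1.

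**Step 3: is operating kept apart from rating?**

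Sections 4.11 and 4.13 require unaware assessors, and the Section 8 symbols point to a research associate who treats and a doctor who rates. That is the intended split. No passage says that an operator may not rate, or that a rater may not operate or see the screen.

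**Step 4: participant blinding, a separate matter.**

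Section 4.4.2 says no dose differs perceptibly from sham and gives skin heating as its example. Section 4.20.1 says the device may cause a slight feeling of heat and lists heat at the application site among reported events. The two statements do not agree.

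**The case against.** The strongest reply is that rater blinding is already covered. Section 4.13 requires raters who do not know the allocation, Sections 4.11 and 5.1 blind assessors and doctors, Section 8 separates the two tasks by symbol, Sections 4.4 and 4.9.2 give delivery to trained personnel, and Section 6.5 allows a designee. A rater who had seen the arm would already breach Section 4.13, and no passage assigns both tasks to one person. On this view Section 3.2 holds a drafting error and little more.

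Much of that stands. It shows what is intended, and it limits what can be claimed. It does not remove the contradiction about the operator. Nor does it supply a rule that keeps a principal investigator or doctor who applies the laser, as Section 6.5 allows, from also rating. A symbol legend is not such a rule.

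Some stronger readings are tempting, but the protocol does not support them:

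- **Raters will be unblinded.** The text permits it in places but does not prescribe it.
- **The number of ratings at risk can be capped** by counting HAMD-17 assessments after the first session. Section 4.4.1 has the treatment number obtained at each visit before the laser, and nothing places the visit 1 rating before that step, so such a count is not an upper bound.
- **Section 6.4 counts the principal investigator among the delivery staff.** Its phrase about other staff can equally mean staff apart from the investigator.
- **Section 4.17.3 makes the investigator the general judge of device-relatedness.** The sentence that names the investigator's judgement concerns only immediate reporting of unanticipated events, and the general grading names no role.

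**Conclusion.** The point holds in two parts, with different certainty.

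- **Operator: high confidence.** The Section 3.2 statement is wrong as written and is contradicted by the rest of that section and by Sections 1 and 5.1. This rests on the displayed mode numbers being those in the printed list; the protocol says nothing to the contrary.
- **Investigators and raters: moderate confidence.** The protocol intends blinded raters and a research associate as operator, but Sections 4.4.1, 4.20.1 (with 4.9.2) and 6.5 let someone declared blinded see the arm, and no rule keeps operating and rating apart. This is an unclosed gap, not proof that blinding fails.

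The size of any bias is unknown, and the protocol gives nothing from which to estimate it. The matter should be fixed because the primary endpoint is doctor-rated. It does not make the design unworkable. The heat statements are a smaller, separate inconsistency about participant blinding.

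**What to change.** 1. Delete the claim in Section 3.2 that the operator is blinded. Make Sections 3.2, 4.4.1 and 4.4.2 agree with Sections 1 and 5.1: operators aware; participants, investigators and raters blinded.
2. Amend Sections 4.4.1, 4.4.2, 4.20.1 and 6.5 so that the laser is applied by a trained delegate who does not rate that participant. State that anyone who operates the device, or sees the console, mode or group, does not rate HAMD-17, QIDS-C or CGI-S for that participant and does not disclose the mode. Leave the safety actions in Sections 4.17.2 and 6.4.1 and the emergency unblinding in Section 4.4.3 untouched. The rule should not extend to adverse event relatedness or withdrawal decisions, because it would then catch an investigator unblinded for safety and interfere with stopping treatment at a session.
3. Move the mode-to-arm list from Section 3.2 to an operator-only document. This is a partial safeguard: it helps for staff who have not yet read the list and cannot re-blind those who have.
4. Separately, reconcile the statements on perceptible heat in Sections 4.4.2 and 4.20.1.

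**Cost.** A protocol amendment and a short operator document. Sites must keep operator and rater apart among existing staff, with a trained operator who does not rate that participant at each session. The Section 8 table already implies that split. None of these steps requires a change to the device.

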3.3 Overview of Positron Emission Tomography (PET scan)

The main metabolite used by the brain to obtain ATP in mitochondrial oxidative processes is glucose, although this organ constitutes 2% of the body weight, it is known to use 20-25% of the total circulating glucose. We consider that, therefore, it becomes the ideal vehicle to determine metabolic rates in the different regions of the brain.

Positron emission tomography (PET) is a nuclear medicine study that provides maps indicating metabolic activity, especially glucose metabolism in different tissues and lesions (Ropper et al. 2008), using a radiopharmaceutical that is the union of a drug or physiological substance with known pharmacokinetics and pharmacodynamics with a positron-emitting radioactive atom. On the one hand, the drug has a known biodistribution and, on the other hand, the positron-emitting atom indicates the location of this drug after tracking in a PET camera. Because the PET system lacks an anatomical reference to determine the exact location of these abnormalities, PET is currently fused to a computed tomography (CT) system (Roldán-Valadez et al. 2008). The most frequently used radiopharmaceutical is fluorodeoxyglucose, which is 18F-labeled glucose, known by the acronym 18FDG.

The use of positron emission tomography/computed tomography with 18F-fluorodeoxyglucose

Near Infrared Transcranial Laser Therapy in Subjects with Major Depressive Disorder: A study of Dosing with Laser.

(PET/CT with 18F-FDG) as a means of determining brain metabolism is proposed, not only globally but regionally. This tool has already been used in different neuropsychiatric conditions, such as: cognitive impairment, dementia and Parkinson's disease, as well as in patients with affective disorders, such as major depressive disorders (Lyra et al. 2020; Sacher et al. 2012). There is evidence that depression is associated with deficits in brain metabolism.

There is a growing consensus that there are a number of brain areas that are involved in depression. PET shows increased glucose metabolism in the anterior cingulate area, specifically in the right pregenual and subgenual regions (Sacher et al. 2012).

The anterior cingulate cortex has a crucial role in initiation, motivation and goal-directed behavior, thus playing a key role in depressive disorders (Alexopoulos et al. 2008), changes in these areas, as determined by PET CT is even useful to identify eventual responders after starting a treatment (De Crescenzo et al. 2016).

4. Research Plan

4.1 Study Aims

Primary Aim:

A. To evaluate and compare the effect(s) of each of the four doses of NIR-TLT on depressive symptomatology: antidepressant effect, in patients with major depressive disorder (MDD).

Hypothesis 1: Total HAM-D 17 scale scores will vary in a NIR-TLT dose-dependent manner, with BPW dose being more effective.

We also expect to be able to estimate the effect size of the antidepressant action as a function of the irradiance applied to the NIR-TLT skin, with the BPW dose being more effective.

Secondary Aims:

B. Compare safety and tolerability at each dose of NIR-TLT.

Hypothesis 2: The doses of NIR-TLT tested in this study will be safe and well tolerated by patients with MDD, as assessed by SAFTEE-SI and reports of serious adverse events. We do not anticipate dose-dependent differences in reported side effects.

C. To compare the effect(s) of each of the four doses of NIR-TLT on brain electrophysiology.

Exploratory Aim:

D. To describe the findings visualized in PET, related to the brain metabolism of the participants, before and at the end of the intervention under study.

4.2 Rationale for the use of the EXPi device:

Transcranial photobiomodulation (t-PBM) with near infrared (NIR) laser therapy has emerged as a possible antidepressant treatment in both animal models (Mohammed et al.2016; Salehpour 2016-2017; Xu et al.2017; Wu et al.2012), and in human studies (Cassano 2015- 2017; Caldieraro et al.2018) t-PBM. NIR appears to increase brain metabolism (by activating the cytochrome C oxidase in the mitochondria), to increase neuroplasticity and to modulate the

Near Infrared Transcranial Laser Therapy in Subjects with Major Depressive Disorder: A study of Dosing with Laser.

endogenous opioids, while decreasing inflammation and oxidative stress. (Chung et. al. 2012; Yu et. al. 1997; Oron et al. 2007, Mochizuki et al. 2002) t-PBM penetrates deep into the cerebral cortex, modulates cortical excitability, and improves cerebral perfusion and oxygenation. The safety of t-PBM has been studied in a sample of 1410 acute stroke patients, with no significant difference in adverse event rates between t-PBM and sham exposure. (Hacke et al. 2014; Lamp et al. 2007, Zivin et al. 2009) Uncontrolled studies suggest an antidepressant effect of t-PBM in subjects suffering from MDD (Cassano 2015-2017; Caldieraro et al. 2018).

Different devices have been used in the study of the effects of near infrared radiation (NIR) treatment in humans. We decided to use a Litecure device specifically adapted for this study to allow NIR-TLT testing of different doses in a controlled manner.

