5.3 Sample Size

The sample size was determined using G Power software version 3.1, considering a calculation by double mean difference with common standard deviation, assuming a significance level of 0.05 and 90% power. The parameters used were obtained from page 7 (section "Antidepressant effect according to clinician-rated measurement") of the previous ELATED-2 study (Cassano et al., 2018), where the mean difference of the HAM-D17 score for the experimental group was -10.8 ± 7.55 and for the control group 4.4 ± 6.65 ; such data identify a double difference of 6.4 with common standard deviation of 7.091. With this information, a total sample of 112 participants is obtained, taking into consideration a 20% loss rate. Each group will have 28 participants.

With $n=112$, in 4 groups in a longitudinal design, we estimated a power of 90% to differentiate ($\alpha=0.05$) the therapeutic effect of the dose, giving an antidepressant effect and an effect variance equivalent to that obtained in participants who completed the ELATED-2 study for all groups (Cassano et al., 2018b)

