5.5 Efficacy and Safety Analysis for the Aims

It will be carried out as follows:

A. Antidepressant effect of NIR-TLT doses:

To compare the antidepressant effects of NIR-TLT doses, mean changes in HAM-D 17 scores (for evaluation of the Primary Assessment Criteria) and QIDS-C and CGI-S (for evaluation of the Secondary Assessment Criteria), will be performed for each dose at 3 time points (visit 1, visit 9 and visit 18) will be compared using a repeated measures ANCOVA. A significant ANCOVA interaction in mean score changes between groups will be taken as indicating that the groups have different antidepressant efficacy. If significant ANCOVA interactions are found, paired samples t-tests will be used to explore differences between scores/groups.

Both the full analysis and the analysis by intention will be performed to analyze the severity of depression at the endpoint. Patient attrition and dropout will be analyzed. The possible

Transcranial Near Infrared Laser Therapy in Subjects with Major Depressive Disorder: A Laser Dosing Study.

differences between treatment groups in dropouts will be examined with Fisher's exact test.

B. Brain electrophysiological effect of NIR-TLT doses:

To compare the effects of NIR-TLT doses on brain electrophysiology, changes in EEG spectral power in all spectral bands for each dose at 3 time points (visit 1, visit 9, and visit 18) will be compared using a repeated measures ANCOVA. A significant ANCOVA interaction in mean score changes between groups will be taken as indicating that the groups have different effects. If significant ANCOVA interactions are found, paired samples t-tests will be used to explore differences between groups.

C. Safety and tolerability of NIR-TLT doses:

To compare the safety and tolerability of NIR-TLT doses, mean changes iSAFTEE-SI scores at 3 time points (visit 1, visit 9, and visit 18) will be compared using a repeated measures ANOVA. A significant ANOVA interaction in mean score changes between groups will be taken as indicating that the NIR-TLT doses have different tolerability. If significant ANOVA interactions are found, paired samples t-tests will be used to explore differences between groups.

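### The 90% power in section 5.3 was derived for active versus sham; the directional part of Hypothesis 1, that pulsed light is more effective, has no planned difference and no designated test

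*Protocol*

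**What the plan says.** **Hypothesis.** Protocol 4.1, repeated in 5.2, gives the primary hypothesis as "Total HAM-D 17 scale scores will vary in a NIR-TLT dose-dependent manner, with BPW dose being more effective". It names no comparator for BPW and no size of advantage.

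**Arms.** Section 3.2 lists BCW, BPW-1, BPW-2 and SHAM. The three active modes have the same irradiance (350 mW/cm²), exposure time (429 s) and energy (3.6 kJ). They differ in time format: continuous, pulsed at 10 Hz, or pulsed at 40-50 Hz.

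**Sample size.** Section 5.3 describes the method as "considering a calculation by double mean difference with common standard deviation, assuming a significance level of 0.05". The pilot inputs are that "the mean difference of the HAM-D17 score for the experimental group was -10.8 ± 7.55 and for the control group 4.4 ± 6.65", and "such data identify a double difference of 6.4 with common standard deviation of 7.091". With 20% loss this gives 112, or 28 per group. A second paragraph says that "in 4 groups in a longitudinal design, we estimated a power of 90% to differentiate" the effect of the dose, on the basis of a pilot effect and "an effect variance equivalent to that obtained in participants who completed the ELATED-2 study for all groups".

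**Analysis.** In 5.5 A, a significant interaction in the repeated-measures ANCOVA "will be taken as indicating that the groups have different antidepressant efficacy". If it is significant, t-tests explore the differences. No contrast between BPW and BCW is singled out.

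**The concern.** Because the active modes share irradiance, time and energy, saying that BPW is more effective adds something beyond active versus sham only as a claim about pulsed against continuous light. The pilot had one active arm and a sham arm (3.1), so its 6.4 points carry no information about that difference, and the protocol gives no other figure for it. A reader of 5.3 would still take the 90% as covering the primary hypothesis.

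Two things are at stake. A null BPW-BCW result would be read as evidence from a 90%-powered trial when it may be uninformative. A positive one would come from a comparison that was not designated in advance, reached after an omnibus test that sham alone can carry.

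**Working it through.** **Inputs.** Difference 6.4, SD 7.091, alpha 0.05, power 90%, loss 20%, four equal groups (5.3). Completer results 15.7 ± 4.4 (n = 6) and 6.1 ± 7.9 (n = 7) (3.1). Evaluable number per arm: 22 (28 less 20%, rounded down) or 28. Both are shown because 4.7 describes the 112 as analyzable while 5.3 already allows for loss.

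**1. The plan's figure.** 10.8 − 4.4 = 6.4, reading the control change as a decrease.
- One-sided: n = 2 × (1.645 + 1.282)² × 7.091² / 6.4² = 21.03, so 22 per arm (noncentral t also gives 22, power 90.3%). 22 / 0.8 = 27.5, so 28; 4 × 28 = 112. This matches.
- Two-sided: 25.8, so 26 per arm (27 by the t distribution). After loss this is 33 or 34 per arm, a total of 132 or 136. This does not match.
- Two-sided power for 6.4 points is 83% with 22 per arm and 91% with 28.

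**2. Omnibus comparison.** Take sham at 0 and the three active arms at 6.4, so the grand mean is 4.8. Then λ = n × (4.8² + 3 × 1.6²) / 7.091² = n × 30.72 / 50.28. This is 13.4 for n = 22 and 17.1 for n = 28. Power of the four-group F test is 87% and 94%.

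**3. BPW versus BCW.** The protocol gives no difference, so a range is assumed. Noncentrality = (Δ / SD) / √(1/n₁ + 1/n₂); t-test, two-sided 5%, SD 7.091. Example for Δ = 3.2 (half of 6.4), 22 v 22: 0.4513 / √(2/22) = 1.50 against a critical value of 2.02, power 31%.

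| Assumed Δ | 22 v 22 | 28 v 28 | BPW pooled, 44 v 22 | BPW pooled, 56 v 28 |
|---|---|---|---|---|
| 6.4 | 83% | 91% | 93% | 97% |
| 4.8 | 59% | 70% | 72% | 82% |
| 3.2 | 31% | 38% | 40% | 49% |
| 1.6 | 11% | 13% | 14% | 16% |

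For 90% power, a single pair needs a difference of 7.1 points (22 per arm) or 6.3 points (28 per arm), about the whole active-sham effect.

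**4. Completer inputs.** Difference 15.7 − 6.1 = 9.6. Pooled SD = √[(5 × 4.4² + 6 × 7.9²) / 11] = 6.55. At half the effect (4.8 points), power is 66% (22 per arm) or 77% (28 per arm) for one pair, and 79% or 88% with BPW pooled.

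**5. Follow-up after the omnibus test.** Simulation, 60,000 trials, three active arms equal and each 6.4 better than sham. One change score stands in for the interaction, followed by independent two-sample t-tests at 0.05 without adjustment. The omnibus test passes in about 87% of trials (22 per arm) or 94% (28 per arm). Counting trials in which it passes and the pair is significant:
- at least one active-active pair falsely different: about 12%;
- BCW different from a BPW arm, in either direction: about 9%;
- a BPW arm falsely better than BCW: about 4%.

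If all four arms are equal, the omnibus test holds the error for any pair at about 5%.

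**The case against.** **The 90% may refer to the omnibus test.** The protocol counts SHAM as one of its four doses, and the power sentence speaks of four groups. On that reading 87% to 94% is close to the claim. This stands, and it confines the point to the directional part of the hypothesis.

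**The inputs may be too pessimistic.** The second power sentence rests on pilot completers, whose larger effect and smaller SD give the higher figures in step 4. The words at the end of that sentence may also mean only a common variance, not equal effects in every active arm. Both stand. It would therefore be too strong to infer that the protocol assumes a zero BPW-BCW difference or that power for it does not exist. What is missing is any planned difference to support a figure.

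**The follow-up may be adjusted.** A reader might infer that pairwise testing is unadjusted and will rank equal arms by chance. The protocol only names no adjustment, describes the step as exploratory, and leaves room for a statistical analysis plan that is not shown. The 12% also counts any active pair, including BPW-1 against BPW-2 and cases where BCW looks better. A false finding in the hypothesised direction is about 4%. The simulation uses independent t-tests, whereas 5.5 A names paired ones, which do not suit parallel groups. The error-rate argument is therefore secondary.

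**Pooling is a choice.** The two BPW arms differ in pulse rate. This is true, although Hypothesis 1 itself treats BPW as one dose.

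**Conclusion.** The point holds in limited form. The 90% in 5.3 comes from a one-sided active-versus-sham calculation and cannot be carried over to the claim that BPW is more effective. Power for that claim is 31% to 49% at an assumed 3.2 points with SD 7.091, and 66% to 88% at 4.8 points with the completer SD, depending on evaluable numbers and on pooling. Two-sided at SD 7.091, it reaches 90% for a single pair only if BPW beats BCW by about as much as active beat sham in the pilot.

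The documents do not support saying that the trial is underpowered for its whole primary aim, since the four-group comparison is roughly adequate. Nor do they support calling the pairwise follow-up uncontrolled.

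Assumptions: the BPW-BCW differences are illustrative, a change score at one visit replaces the repeated-measures interaction, and any gain in precision from baseline adjustment is ignored because the protocol gives no correlation.

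**What to change.** **Section 5.3.** Limit the power statement to active versus sham and state its sidedness: 90% one-sided with 22 evaluable per arm; two-sided, 83% with 22 and 91% with 28. The 90% should not stay without that qualification. Add that the trial is not powered at 90% for BPW versus BCW, and give power over a range of assumed differences, as in the table above.

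**Section 5.5 A.** Name one contrast for the directional hypothesis: BPW-1 and BPW-2 pooled versus BCW, on HAM-D17 change to visit 18, with a 95% confidence interval. Show the two BPW arms separately as well, and label the other active-active pairs descriptive.

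**Cost.** Only wording changes; arms, visits and numbers stay as they are. The stated figure becomes less favourable, and pooling assumes that the two pulse rates act alike, which is why the separate estimates should be shown.
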